12.2.1. Definitions of Assessment Windows for Analyses

The daily itch/pruritus NRS score (based on Item #1 of Daily Sign and Symptom Severity Diary) is recorded daily and will be averaged for every week.

The 7-days average score will be calculated as:

$$\frac{\sum(\text{Daily itch/pruritus NRS score in 7 days})}{\text{Total number of days Daily itch/pruritus NRS score is recorded in 7 days}^*}$$

- If a subject is missing more than 3 daily itch/pruritus NRS scores out of the 7 days, then the average NRS score for that week will be recorded as missing.
- 7-days average score for baseline visit will be calculated based on 7 days prior to the day of dosing (i.e., from Day -7 to Day -1).
- 7-days average score for Week 1 visit will be 7 days after the day of dosing (i.e., from Day 1 to Day 7).
- Similarly, for Week 2 (from Day 8 to Day 14) and henceforth till Week 20.

12.3. Appendix 3: Study Phases and Treatment Emergent Adverse Events

12.3.1. Study Phases

Safety assessments and events will be classified according to the time of occurrence relative to the first dose of investigational product.

The on-treatment phase for the presentation of exposure, adverse event and concomitant medications is defined as being from the day of the first administration to the day of the last administration of study treatment + another 28 days inclusive.

Treatment Phase	Definition
Pre-Treatment	Date < IP start date
On-Treatment	Event onset date is on/after IP start date & on/before IP stop date + 28 days (IP Start Date ≤ Date ≤ IP Stop Date + 28 days)
Post-Treatment	Event onset date is after the IP stop date + 28 (Date > IP stop date + 28)
IP = Investigational Product = Study Treatment	

12.3.1.1. Study Phases for Efficacy Assessments

Efficacy assessments and events will be classified according to the time of occurrence relative to the study periods defined below:

Period	Definition
Study Treatment Period	Date ≤ Week 16 date (or date of withdrawal from the study, if prior to Week 16)
Follow-up Period	Week 16 date < Date ≤ Week 20 date (or date of withdrawal from the study, if between Week 16 and 20)

12.3.2. Treatment Emergent Flag for Adverse Events

Flag	Definition
Treatment Emergent	If AE onset date is on or after treatment start date & on or before treatment stop date. (plus 28 days) (Study Treatment Start Date ≤ AE Start Date ≤ Study Treatment Stop Date + 28)

NOTES:

- If the study treatment stop date is missing, then the AE will be considered to be On-Treatment.
- Time of study treatment dosing and start/stop time of AEs should be considered, if collected.

12.4. Appendix 4: Data Display Standards & Handling Conventions

12.4.1. Reporting Process

Software	

 The currently supported versions of SAS software 9.4 or higher will be used. 	
Reporting Area	
HARP Server	: uk1salx00175.corpnet2.com
HARP Compound	: sb240563\mid205050\final_02
QC Spreadsheet	: sb240563\mid205050\ final_02\documents
Analysis Datasets	

 Analysis datasets will be created according to CDISC standards (SDTM IG Version 3.1.3 & ADaM IG Version 1.0]. For creation of ADaM datasets (ADCM/ADAE), the same version of dictionary datasets will be implemented for conversion from SI to SDTM. 	
Generation of RTF Files	

 RTF files will be generated for SAC. 	

12.4.2. Reporting Standards

General

 The current GSK Integrated Data Standards Library (IDSL) will be applied for reporting, unless otherwise stated (IDSL Standards Location: https://spope.gsk.com/sites/IDSLLibrary/SitePages/Home.aspx): 
 4.03 to 4.23: General Principles 5.01 to 5.08: Principles Related to Data Listings 6.01 to 6.11: Principles Related to Summary Tables 7.01 to 7.13: Principles Related to Graphics
Formats

 GSK IDSL Statistical Principles (5.03 & 6.06.3) for decimal places (DP's) will be adopted for reporting of data based on the raw data collected, unless otherwise stated. Numeric data will be reported at the precision collected on the eCRF. The reported precision from non eCRF sources will follow the IDSL statistical principles but may be adjusted to a clinically interpretable number of DP's.
Planned and Actual Time

 Reporting for tables, figures and formal statistical analyses: 
 Planned time relative to dosing will be used in figures, summaries, statistical analyses and calculation of any derived parameters, unless otherwise stated. The impact of any major deviation from the planned assessment times and/or scheduled visit days on the analyses and interpretation of the results will be assessed as appropriate. Reporting for Data Listings: 
 Planned and actual time relative to study drug dosing will be shown in listings (Refer to IDSL Statistical Principle 5.05.1). Unscheduled or unplanned readings will be presented within the subject's listings.

Unscheduled Visits	

 • Unscheduled visits will not be included in summary tables and/or figures. • All unscheduled visits will be included in listings. 	
Descriptive Summary Statistics	
Continuous Data	Refer to IDSL Statistical Principle 6.06.1
Categorical Data	N, n, frequency, %
Graphical Displays	

 • Refer to IDSL Statistical Principals 7.01 to 7.13. 	

12.4.3. Reporting Standards for Pharmacokinetic

Pharmacokinetic Concentration Data	
Descriptive Summary Statistics, Graphical Displays and Listings	Refer to IDSL PK Display Standards. Refer to IDSL Statistical Principle 6.06.1. Note: BLQ Concentration values will be imputed as per GUI_51487 for descriptive summary statistics and summarized graphical displays only.

12.5. Appendix 5: Derived and Transformed Data

12.5.1. General

Multiple Measurements at One Analysis Time Point

 If there are two values within a time window (as per Section 12.2.1) then the latest assessment will be used. Participants having both High and Low values for Normal Ranges at any post-baseline visit for safety parameters will be counted in both the High and Low categories of “Any visit post-baseline” row of related summary tables. This will also be applicable to relevant Potential Clinical Importance summary tables.
Study Day

 Calculated as the number of days from Randomization Date: 
 Ref Date = Missing → Study Day = Missing Ref Date < Randomization Date → Study Day = Ref Date – Randomization Date Ref Date ≥ Randomization Date → Study Day = (Ref Date – Randomization Date) + 1

12.5.2. Study Population

Extent of Exposure

 Number of days of exposure to study drug will be calculated based on the formula: Duration of Exposure in Days = (Treatment Stop Date – Treatment Start Date) + 29 Participants who were randomized but did not report a treatment start date will be categorised as having zero days of exposure. On-treatment phase will be calculated based on the formula: On-Treatment Phase = (Treatment Stop Date – Treatment Start Date) + 29

12.5.3. Efficacy

Efficacy
Investigators Global Assessment (IGA)

CCI - This section contained Clinical Outcome Assessment data collection questionnaires or indices, which are protected by third party copyright laws and therefore have been excluded.

 A Responder is defined as a subject who has an IGA score of 0 or 1 and a minimum 2-grade improvement from baseline. This is calculated for each study visit. As per protocol, a non-responder imputation will be used for all early withdrawal subjects where

Efficacy

subject's data will be imputed as a Non-Responder for all post withdrawal visits. This imputation will be used for summary and analysis table for primary and secondary endpoints.

- The observed IGA score classifications will be used for each visit. For all early withdrawal subjects the data from Post-Treatment 1/Post-Treatment 2/Early Withdrawal visits will be slotted using the algorithm detailed in Section 12.2
- AD flare/relapse for IGA is defined as IGA score of 3 or 4 after achieving an IGA score of 0 or 1 and at least a 2- grade improvement from the baseline.

Body Surface Area

Body Region	% Involvement (0-100% each area)	% Involvement x Proportionality Multiplier	Regional % BSA Involvement
Head and neck		___ x 0.1	
Upper extremities		___ x 0.2	
Trunk		___ x 0.3	
Lower extremities		___ x 0.4	
Total Involved % BSA (sum of the 4 area values) =			_____

EASI

CCI - This section contained Clinical Outcome Assessment data collection questionnaires or indices, which are protected by third party copyright laws and therefore have been excluded.

- The observed EASI data will be used for each visit. For all early withdrawal subjects, data from Post-Treatment 1/Post-Treatment 2/ Early Withdrawal visits will be slotted using the algorithm detailed in Section 12.2.
- AD flare/relapse for EASI is defined as increase in EASI score of ≥25% from Baseline.

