9.4. Key Elements of Analysis Plan

9.4.1. Primary Analyses

The primary efficacy endpoint is the IGA response rate at week 16. The observed response rate and difference between mepolizumab and placebo and the 80% credible interval for the response rate and the difference in response rate will be presented. The posterior probability that the IGA response rate for mepolizumab is 40% or greater and that the improvement over placebo is at least 15 percentage points will be calculated.

Subjects withdrawing prematurely from the study prior to the Week 16 visit will be assumed to be non-responders.

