1. INTRODUCTION

The purpose of this reporting and analysis plan (RAP) is to describe the analyses to be included in the Clinical Study Report for Protocol:

Revision Chronology:		
2015N268158_00	2016-AUG-25	Original
2015N268158_01	2016-DEC-26	Amendment No. 1

 Protocol amendment 1 includes recommendations from the US Food and Drug Administration (FDA) and other clarifications. 		
2015N268158_02	2017-JUN-22	Amendment No. 2

 The addition of administrative interim analyses to enable review of subject efficacy and safety data summaries. Minor clarifications regarding: collection of ECGs in triplicate for all ECG timepoints; general order of study procedures; checks for BSA and EASI eligibility utilizing eCRF auto calculated totals at Screening and Baseline visits. Increase in anticipated number of subjects screened from approximately 75 subjects to approximately 140 subjects (no change in target number of subjects randomized). Reminders inserted into the study schematic and Time and Events tables, indicating no IP dose will be administered at Week 16 and Week 20. Removed requirement for subject data entry into the Daily Sign and Symptom Severity Diary for at least 7 consecutive days immediately prior to the Baseline visit. 		

Following a formal interim analysis (10-NOV-2017) after approximately 50% of subjects were randomised and had the opportunity to complete the Week 8 visit, the study met the planned futility stopping criteria and the study was terminated. As a result of the study being terminated, only a sub-set of planned protocol defined objectives and endpoints will be included for the final reporting.

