3.2. Final Analyses

The final planned primary analyses will be performed after the completion of the following sequential steps:

1. All participants who had enrolled into the study prior to the termination of the study as defined in the protocol will be part of final analysis.
2. All required database cleaning activities have been completed and final database release (DBR) has been declared by Data Management.
3. All protocol deviations have been confirmed.
4. All criteria for unblinding the randomisation codes have been met.
5. Source Data Lock has been declared by Data Management.
6. Randomisation codes have been distributed according to RandAll NG procedures.
7. Database freeze has been declared by Data Management.

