12.9.5. Efficacy Tables

Efficacy: Tables					
No.	Population	IDSL/ Example Shell	Title	Programming Notes	Deliverable
IGA					
2.1.	ITT	EFF_T1	Bayesian Posterior Probability for Comparison between Mepolizumab and Placebo	Note: Non-Responder imputation will be used	SAC
2.2.	ITT	EFF_T2	Number (%) of Participants in Each Category of the Investigator's Global Assessment Scale at Each Visit		SAC
2.3.	ITT	EFF_T3	Summary of Proportion of Participants with IGA Score of 0 or 1 and at Least a 2-Grade Improvement from Baseline at Each Visit	Note: Non-Responder imputation will be used	SAC
EASI					
2.4.	ITT	EFF_T4	Summary of Change from Baseline/Percent Change from Baseline in EASI Score at Each Visit	Note: CFB, %CFB in bylines	SAC
2.5.	ITT	EFF_T4	Summary of Change from Baseline/Percent Change from Baseline in EASI Score at Each Visit by Baseline Blood Eosinophil Count Quartiles	Note: Include Quartiles categories as $\leq Q1(x)$, $>Q1(x)$ - $\leq Q2$, $>Q2(x)$ - $\leq Q3(x)$ and $>Q3(x)$. Include all quartiles value(x)	SAC
2.6.	ITT	EFF_T5	Summary of Proportion of Participants with $\geq 50\%$ and $\geq 75\%$ Improvement in EASI Score from Baseline at Each Visit	Note: $\geq 50\%$, $\geq 75\%$ improvement in bylines.	SAC
Patient Reported Outcomes					
2.7.	ITT	EFF_T4	Summary of Change from Baseline in Weekly Average of Daily Itch/pruritus NRS Score (based on Item #1 of Daily Sign and Symptom Severity Diary) at Each Visit	Includes Baseline values. Note: Mean change from baseline will be presented to only Week 4, 8, 12, 16 and 20	SAC

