12.10. Appendix 10: Example Mock Shells for Data Displays

Example: POP_T1
 Protocol: 205050
 Population: Safety

Page 1 of n

Table 1.10
 Summary of Exposure to Study Treatment

		Placebo SC (N=xx)	Mepolizumab 100mg SC (N=xx)
Treatments Administered	n	68	68
	Mean	11.6	12.7
	SD	3.30	1.33
	Median	13.0	13.0
	Min.	2	4
	Max.	14	14
Number of Treatments	1	0	0
	2	2 (3%)	0
	3	3 (4%)	0
	4	3 (4%)	1 (1%)
Number of Days on Treatment	n	68	68
	Mean	330.8	357.2
	SD	91.43	37.39
	Median	365.0	365.0
	Min.	57	114
	Max.	394	392

CONFIDENTIAL

205050

Note: Number of Days on Treatment = (Treatment Stop Date - Treatment Start Date) + another 28 days inclusive.

Example: EFF_T1
 Protocol: 205050
 Population: Intent-to-Treat

Table 2.1
 Bayesian Posterior Probability for Comparison between Mepolizumab and Placebo

Visit	Treatment	n	Posterior Mean Response Rate (80% Cred Int)	Posterior Median Response Rate (80% Cred Int)	Posterior Mean Difference (80% Cred Int)	Posterior Probability of Response Rate \geq 40%	Posterior Probability of difference of Response Rate \geq 15%
Week 16	Mepolizumab 100 mg SC	xx	xx.xx (xx.xx, xx.xx)	xx.xx (xx.xx, xx.xx)	xx.xx (xx.xx, xx.xx)	xx.xx	xx.xx
	Placebo SC	xx	xx.x x (xx.xx, xx.xx)	xx.xx (xx.xx, xx.xx)			

Note: A Responder is defined as a subject who has an IGA score of 0 or 1 and a minimum 2-grade improvement from baseline. If a subject withdraws early from the study the due to lack of efficacy or disease progression, then all weeks after withdrawal they are assigned to be a non-responder.

Note: 0=Clear; 1=Almost Clear; 2=Mild; 3=Moderate; 4=Severe.

Example: EFF_T2
Protocol: 205050
Population: Intent-to-Treat

Table 2.2

Number (%) of Subjects in Each Category of the Investigator's Global Assessment Scale at Each Visit

Visit	Category	Placebo SC (N=XX)	Mepolizumab 100 mg SC (N=XX)
Day 1	n	XX	XX
	Clear	XX (XX%)	XX (XX%)
	Almost Clear	XX (XX%)	XX (XX%)
	Mild	XX (XX%)	XX (XX%)
	Moderate	XX (XX%)	XX (XX%)
	Severe	XX (XX%)	XX (XX%)

Programming note: Repeat for all study visits

Example: EFF_T3
 Protocol: 205050
 Population: Intent-to-Treat

Table 2.3

Summary of Proportion of Subjects with an IGA Score of 0 or 1 and at Least a 2-Grade Improvement from Baseline at Each Visit

Visit	IGA score of 0 or 1 and at least a 2-grade improvement	Placebo SC (N=XX)	Mepolizumab 100mg SC (N=XX)	Proportions Difference	90% CI for the Proportions Difference
Week 4	n	XX	XX		
	Yes	XX (XX%)	XX (XX%)	XX%	(XX.X%, XX.X%)
	No	XX (XX%)	XX (XX%)		

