Note: A Responder is defined as a subject who has an IGA score of 0 or 1 and a minimum 2-grade improvement from baseline. If a subject withdraws early from the study the due to lack of efficacy or disease progression, then all weeks after withdrawal they are assigned to be a non-responder.

Note: Day 1 is considered as baseline.

Note: 0=Clear; 1=Almost Clear; 2=Mild; 3=Moderate; 4=Severe.

Programming note: Repeat for all available visits

Example: EFF_T4
 Protocol: 205050
 Population: Intent-to-Treat

Table 2.4

Summary of Change from Baseline/Percent Change from Baseline in EASI Score at Each Visit

Summary: Change from Baseline

Visit		Placebo SC (N=XX)	Mepolizumab 100mg SC (N=XX)
Day 1	n	XX	XX
	Mean	x.x	x.x
	SD	X.XX	X.XX
	Median	x.x	x.x
	Min.	X	X
	Max.	X	X
Week 4	n	XX	XX
	Mean	x.x	x.x
	SD	X.XX	X.XX
	Median	x.x	x.x
	Min.	X	X
	Max.	X	X

Summary: Percentage Change from Baseline

.....[Format as Change from Baseline]

Note: Day 1 is considered as baseline and summarized for absolute value.
 Programming note: Repeat for all available visits and include percent change from baseline

Example: EFF_T5
 Protocol: 205050
 Population: Intent-to-Treat

Table 2.6
 Summary of Proportion of Subjects with $\geq 50\%$ and $\geq 75\%$ Improvement in EASI Score from Baseline at Each Visit

Visit	Improvement in EASI Score from baseline	Placebo SC (N=XX)	Mepolizumab 100mg SC (N=XX)	Proportions Difference	90% CI for the Proportions Difference
Week 4	n	XX	XX		
	$\geq 50\%$ improvement	XX (XX%)	XX (XX%)	XX%	(XX.X%, XX.X%)
	$\geq 75\%$ improvement	XX (XX%)	XX (XX%)	XX%	(XX.X%, XX.X%)

Example: SAF_T1
 Protocol: 205050
 Population: Intent-to-Treat

Table 3.9

Summary of On-Treatment Adverse Events of Special Interest Reported by the Investigator as Meeting the Criteria for Anaphylaxis

	Placebo SC (N=XX)	Mepolizumab 100mg SC (N=XX)
Number of Subjects with Any Event	xx (xx%)	xx (xx%)
Hypersensitivity		
Number of Subjects with Any Event	XX (XX%)	XX (XX%)
Facial Paralysis	XX (XX%)	XX (XX%)
Flushing	XX (XX%)	XX (XX%)
Injection related reaction	XX (XX%)	XX (XX%)
Rash	XX (XX%)	XX (XX%)
Other Systemic Reactions		
Number of Subjects with Any Event	XX (XX%)	XX (XX%)
Facial Paralysis	XX (XX%)	XX (XX%)
Flushing	XX (XX%)	XX (XX%)
Injection related reaction	XX (XX%)	XX (XX%)
Rash	XX (XX%)	XX (XX%)

Example: SAF_T2
 Protocol: 205050
 Population: Safety

Table 3.10
 Summary Profile of On-Treatment Adverse Events Reported by the Investigator as Meeting the
 Criteria for Anaphylaxis

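### The footnotes of primary Table 2.1 and of Table 2.3 misstate the SAP's non-responder rule, and no planned posterior shows what that rule does to subjects cut off by the sponsor's termination

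*SAP*

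**What the plan says.** **The rule.** Protocol 9.4.1: "Subjects withdrawing prematurely from the study prior to the Week 16 visit will be assumed to be non-responders". SAP 12.5.3, citing the protocol, says "a non-responder imputation will be used for all early withdrawal subjects where" the subject is set to non-responder at all visits after withdrawal, for primary and secondary tables. Its next bullet uses observed IGA scores and slots Early Withdrawal and Post-Treatment visit data by the algorithm in SAP 12.2.

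**The displays.** In SAP 12.9.5, Tables 2.1 and 2.3 carry the unrestricted programming note "Note: Non-Responder imputation will be used". Table 2.2 ("Number (%) of Participants in Each Category of the" IGA scale, by visit) carries no such note. The footnotes in shells EFF_T1 and EFF_T3 (SAP 12.10) read differently. Their condition is "If a subject withdraws early from the study the due to lack of efficacy or disease progression". For subjects who meet that condition, and for no others, the footnotes give the consequence: "then all weeks after withdrawal they are assigned to be a non-responder". SAP Table 1, which lists changes from the protocol, declares no change to the rule.

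**Related text.** SAP 7.1.3 says that no intercurrent-event strategy is planned. SAP Table 1 says that the primary objective has no planned sensitivity analysis. SAP 7.1.5.1 literally says that such analyses are planned but names none. The parallel sentence in SAP 10.1.4.1 contains a 'no'.

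**The termination.** SAP 1 reports that "the study met the planned futility stopping criteria and the study was terminated". By SAP 3.2, "All participants who had enrolled into the study prior to the termination of the study as defined in the protocol" enter the final analysis. Sponsor termination appears in the protocol under both 5.4.1 (stop treatment, then 8 weeks of follow-up) and 5.4.2 (withdrawal from the study).

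**The concern.** Two things are wrong, of different kinds.

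The first is a contradiction in the text. A reader of Table 2.1 would be told that only efficacy-related withdrawals were set to failure, when the derivation does this for all early withdrawals without a slotted value. The footnote does not say what happens to the others. Termination by the sponsor falls in that gap.

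The second concerns what is reported. A subject whose follow-up was cut short by a sponsor decision has not shown non-response. Counting such a subject as a failure lowers both arms' rates, so any true difference shrinks if the arms lose similar shares. It also leaves the full denominator in place while the rates move toward zero, so the credible interval gets narrower although information has been lost. Table 2.1 is the only posterior display (Listing 40 is its raw output), so the effect would not be visible in any planned posterior. At stake are the reported Week 16 estimate and its stated precision.

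**Working it through.** **1. Texts side by side**

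| Place | Who becomes a non-responder |
|---|---|
| Protocol 9.4.1 | every study withdrawal before Week 16 |
| SAP 12.5.3 | every early withdrawal, at visits after withdrawal, with slotting under 12.2 |
| SAP 12.9.5, Tables 2.1 and 2.3 | imputation, no restriction on reason |
| SAP 12.10, footnotes of the same two tables | efficacy-related withdrawals only |

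Three places agree and the footnotes stand alone. This part needs no arithmetic.

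**2. Who can lack a Week 16 value**

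The plan gives no figure for this effect and no count of terminated subjects. Write c for the share of an arm cut off by termination without a slotted Week 16 value. Two routes are possible.

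- *Treatment discontinuation (Protocol 5.4.1), visits kept.* After a last dose at Week 12, Post-Treatment Visit 1 falls at Week 16. After a last dose at Week 8, Post-Treatment Visit 2 falls at 8 + 8 = Week 16. Only subjects last dosed at Week 4 or earlier lack a value. Planned size is 50/(1 − 0.10) ≈ 56. The interim required about half, 28, to have had the opportunity to complete Week 8. Final enrolment is not given. With an assumed 18 per arm (36 in all), at most about 36 − 28 = 8 had not reached Week 8, so c is at most about 8/36 = 22%, or 4 per arm if balanced. This treats those 28 as having received the Week 8 dose.
- *Study withdrawal (Protocol 5.4.2).* Only an Early Withdrawal visit between Weeks 12 and 16 would be slotted to Week 16. Here c could be larger.

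**3. Effect on the posterior**

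Assumptions: independent Beta(1,1) priors (the SAP says only non-informative), 18 per arm, and true rates of 10% and 5%. SAP Table 1 speaks of limited responders, but the rates themselves are assumed. The posterior mean of a rate is (x + 1)/(n + 2).

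- Imputed: expected difference = n × 0.05 × (1 − c)/(n + 2).
- Left out: with m subjects remaining per arm, expected difference = m × 0.05/(m + 2).

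At c = 4/18: imputed 18 × 0.05 × 0.778/20 = 3.5 points; left out, m = 14, 14 × 0.05/16 = 4.4 points. Expected interval widths come from enumerating all binomial outcomes with 40,000 posterior draws for each.

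| c per arm | Mean difference, imputed / left out | 80% interval width, imputed / left out |
|---|---|---|
| 0 | 4.5 / 4.5 | 24 / 24 |
| 22% | 3.5 / 4.4 | 22.5 / 27.6 |
| 50% (study-withdrawal route only) | 2.3 / 4.1 | 20.3 / 35.3 |

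The probability of meeting the success rule (posterior probability above 70% that the difference is at least 15 points) stays at or below about 0.05 in every case run with 14, 18 or 22 per arm.

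**4. One possible row of Table 2.1** (assumed 2 against 1 responders, 18 per arm)

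| Handling | Mean difference | 80% interval | P(difference ≥ 15 points) |
|---|---|---|---|
| all imputed, n = 18 | 3/20 − 2/20 = 5.0 | −7.5 to 17.9 | 0.15 |
| 4 per arm left out, n = 14 | 3/16 − 2/16 = 6.3 | −9.2 to 22.1 | 0.23 |
| 6 per arm left out, n = 12 | 3/14 − 2/14 = 7.1 | −10.3 to 24.9 | 0.28 |

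The last row has c = 33% and can arise only under the study-withdrawal route.

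**5. Unequal loss.** If c is 30% on mepolizumab and 10% on placebo, the true 5 points become 7.0 − 4.5 = 2.5. With the shares reversed they become 9.0 − 3.5 = 5.5. The shift can go either way.

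**The case against.** The footnotes sit in example shells that plainly carry material from another study. The exposure shell shows 68 per arm and up to 14 treatments, in a four-dose trial. The operative texts agree with each other, so a programmer is unlikely to be misled. This stands as a reason to call the error minor. It does not make the footnote right, because it is the text drafted to appear under the primary result.

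Non-responder imputation was set in the protocol, no formal testing is planned, and reporting was reduced on purpose after futility. This stands too: the imputed analysis should remain primary.

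The information is largely recoverable. Listings 2 and 3 give reasons for withdrawal and discontinuation, and Listing 27 gives IGA by subject and visit. Table 2.2 shows observed Week 16 counts by arm. So the gap is in the reported posterior, not in the data. Table 2.2 does not fill it, because it also drops efficacy-related withdrawals without a value. Tables 1.1 and 1.2 do not cross reason with whether a Week 16 value exists.

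A reader might infer that every terminated subject is counted as a failure. The documents do not say so: slotting under SAP 12.2 keeps observed values, and the protocol's follow-up visits can supply them. A reader might also infer that the futility stop is in doubt. It rested on Week 8 data, and the final-analysis rule does not touch it.

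**Conclusion.** The footnote contradiction is certain on the text. It has no size of its own, because the footnote is silent on other withdrawals. The dilution and the false gain in precision are real in direction when the arms lose similar shares, but their size is unknown: the number affected is not in the documents and may be zero. If termination was handled as treatment discontinuation with visits kept, the shift is at most about 1 point in the posterior mean difference (3.5 against 4.4) and about 5 points in interval width (22.5 against 27.6), at the assumed 18 per arm and 10% against 5% response. If it was handled as study withdrawal, the shift could be larger. The documents do not say which route applied. They do not support a claim that the study's conclusion would change: no decision depends on the final posterior, and in the low-response cases computed success is improbable under either handling. Severity: minor.

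**What to change.** - Correct the footnotes of Tables 2.1 and 2.3 to the 12.5.3 rule: all early withdrawals are non-responders at post-withdrawal visits unless an observed value is slotted to that visit under 12.2.
- Have SAP 7.1.3 refer to that rule, and correct the sensitivity sentence in 7.1.5.1.
- State whether sponsor-terminated subjects were classed as treatment discontinuations or as study withdrawals.
- Report by arm the number of sponsor-terminated subjects without a slotted Week 16 value.
- If that count is not zero, name in 7.1.5.1 one supportive run of the same model that leaves those subjects out of the Week 16 denominator and treats all other withdrawals as in the primary analysis. If it is zero in both arms, say so and skip the run.

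The cost is a few lines of text, one count and at most one more run of the existing program. The downside of the run is fewer subjects, wider intervals, and the assumption that being cut off by termination is unrelated to response.
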